5 STUDY DESIGN

5.1 Overall Design

Study IM047029 is a Phase 4, prospective, non-randomized, open-label, multicenter clinical study designed to explore the safety, efficacy, effects on QOL, and biomarker response of ozanimod 0.92 mg QD PO administration in participants with moderate to severely active UC in clinical practice.

This clinical study will evaluate ozanimod 0.92 mg QD PO in multiple UC disease subtypes, and with 2 specific cohorts as described in [Section 3.1](#) and [Figure 5.1-1](#).

Participants will undergo screening evaluations to determine eligibility as indicated in the SOA; see [Table 2-1](#)). Participants must meet the eligibility criteria outlined in [Section 6](#) in order to enter the treatment period. Participants must have moderate to severely active UC, defined as a score of 4 through 9 on the 9-point modified Mayo score, in order to enter the treatment period.

Assessments of medical and UC disease history, prior medications, concomitant and UC medications, tobacco/e-cigarette use, baseline (prior to flare) SF, physical examinations, 12-lead electrocardiograms (12-lead ECGs), blood, stool, and urine sample collections, endoscopies with biopsies, Physician's Global Assessment (PGA) ratings, PRO and HRQOL instruments, and other study procedures will be performed as indicated in the SOA ([Table 2-1](#), [Table 2-2](#)). Additional risk-based assessment of cardiac conduction abnormalities, pulmonary function, and/or visual

acuity (including evaluation of the fundus and macula) may also be performed during screening and as appropriate thereafter.

Disease activity assessment for the purpose of eligibility and evaluation of the primary endpoints in both cohorts will be performed using the modified Mayo score instrument ([APPENDIX 3](#)). The modified Mayo score will be calculated using data from the following sources: baseline (prior to flare) SF (patient-reported and recorded by the investigator), daily assessments of SF and RB (PROs recorded in the participant's electronic daily diary), and assessment of mucosal inflammation at endoscopy. The PGA of disease activity (physician-reported) will also be captured at various time points ([Table 2-1](#), [Table 2-2](#)).

Screening will include the assessment of pre-existing cardiac conduction abnormalities by 12-lead ECG. Investigators should consider cardiology consultation if conduction abnormalities are identified on the 12-lead ECGs, or if the participant is receiving concomitant medications (see [Table 7.7-2](#)) that have the potential to decrease their heart rate (HR).

Participants who have a history of uveitis, diabetes mellitus, macular edema or other retinal disease will have ophthalmic evaluation of the fundus, including the macula, prior to study intervention, in order to exclude macular edema.

[figure not shown]
Antibodies to varicella zoster virus (VZV) will be tested during the screening period. Participants must have documentation of positive VZV immunoglobulin G (IgG) antibody status at screening or complete VZV vaccination prior to the first study intervention administration.

- 1) No live or live-attenuated vaccine within 4 weeks prior to study intervention administration. Pregnancy will be excluded in women of childbearing potential (WOCBP) prior to the first study intervention administration.

All eligible participants will receive open-label ozanimod 0.92 mg QD PO, per product label, during the treatment period ([Table 7.1-1](#)). Ozanimod titration will occur during the first 7 days of study intervention exposure, per label ([Table 7.1-2](#)). Once study intervention (ie, ozanimod) has been titrated up to 0.92 mg QD PO (Day 8), further dose escalation is not allowed.

The study design schematic is presented in Figure 5.1-1.

Figure 5.1-1: Study Design Schema

E, endoscopies and biopsies; ES, endoscopic subscore; EOT, end of treatment.

^a For participants who prematurely discontinue from the study, if possible, the EOT visit and follow-up visit should be conducted so that data can be collected at the time of study discontinuation and follow-up and for any further evaluations that need to be completed.

^b Screening endoscopy (colonoscopy or sigmoidoscopy) may be performed within 60 days prior to the first study intervention administration. Photographic evidence of ES ≥ 2 must be available for study inclusion, as per eligibility criteria. In the event that historic endoscopic data is used as a part of screening, historic histopathologic tissue will not be needed to be collected.

^c Ozanimod titration will occur during the first 7 days of study intervention exposure, per label (Table 7.1-2). Participants will receive a phone call on Day 5 (when titrating their dose from 0.23 mg to 0.46 mg) and again on Day 8 (when titrating their dose from 0.46 mg to 0.92 mg) as a reminder about the dose adjustment. If required, an unscheduled visit can be planned anytime during the treatment period. Data regarding study procedures conducted at such unscheduled visits (eg, blood, stool, and urine tests; safety assessments) will be documented in the EDC tool.

5.1.1 Data Monitoring Committee and Other Committees

A Data Monitoring Committee or other review committee will not be used in the study.

5.2 Number of Participants

It is estimated that approximately 250 screened participants in Cohort 1 (advanced therapy-naïve cohort) will be required to achieve 150 treated participants. Similarly, for Cohort 2 (advanced therapy-exposed cohort), it is estimated that approximately 165 participants will be required to achieve 100 treated participants. These enrollment estimates assume a screen failure rate of approximately 40% in each cohort.

If the screen failure rate is higher than expected, enrollment will remain open until the required number of treated participants in each cohort is achieved.

5.3 End of Study Definition

The start of the trial is defined as the first participant's first visit.

The end of the trial is defined as the last participant's last visit or scheduled procedure shown in the SOA ([Table 2-2](#)) for the last participant.

Study completion is defined as the final date on which data for the primary endpoint were or are expected to be collected, if this is not the same.

A participant is considered to have completed the study if he/she has completed the last procedure shown in the SOA ([Table 2-2](#)).

5.4 Scientific Rationale for Study Design

Ozanimod is approved in the US for the treatment of moderate to severely active UC in adults. This approval was based on safety and efficacy data from the induction and maintenance periods of the Phase 3 True North study (NCT02435992)²⁴ and supported by safety and efficacy data from the Phase 2 Touchstone study (NCT01647516)²⁵ and by safety data from 2 randomized, double-blind, double-dummy, active comparator-controlled clinical trials in patients with relapsing forms of MS (NCT02294058 and NCT02047734).^{26,27,28,29} The eligibility criteria for the cohorts within this clinical protocol will be consistent with the approved product label (in the US and other countries, as applicable). The cohorts within this clinical protocol will generate novel data on safety, efficacy, effects on QOL, and biomarker response of ozanimod, as listed in [Section 3.1](#). Consequently, this study will extend the evidence base supporting ozanimod, and these data may be used to further inform the clinical use of ozanimod in the approved UC patient population.

The results of the True North and Touchstone studies demonstrate that equivalence between ozanimod and placebo is no longer present for the multiplicity of controlled endpoints evaluated in those clinical trials.^{28,29} Consequently, Cohort 1 and Cohort 2 will not use placebo control.

The primary endpoint of Cohort 1 and Cohort 2 is assessed using the modified Mayo score instrument, which is a composite of the Mayo score SF, RB, and endoscopic findings subscores.

Consistent with regulatory draft guidance, the instrument is modified from the original description of the Mayo score by the exclusion of friability from an ES of 1 (ES = 1), and the exclusion of the Mayo score's PGA.^{3,30,31} Permutations of the Mayo score are listed in [APPENDIX 3](#). Clinical response, the primary endpoint of Cohort 1 and Cohort 2, has been accepted as a primary endpoint in clinical trials that have supported prior approvals of treatments for UC.³¹ Additional endpoints based on permutations of the Mayo score that will be evaluated in Cohort 1 and Cohort 2 are listed in [Table 4-1](#), [Table 4-2](#), and [Table 4-3](#).

Additional instruments to be assessed in Cohort 1 and Cohort 2 will include (but not be limited to) the following: Geboes score, [REDACTED]

[REDACTED] Inflammatory Bowel Disease Questionnaire (IBDQ), [REDACTED]

([Section 2](#)).

Taken together, the data collected using the instruments described above will facilitate a comprehensive exploration of the effect of ozanimod on UC disease activity (clinical, endoscopic, and histologic), additional UC symptoms, QOL, fatigue, work productivity, and treatment satisfaction.

5.5 Justification for Dose

Ozanimod 0.92 mg QD PO has been approved in the US, Europe, and other countries for the treatment of moderate to severely active UC, following a 7-day titration with 0.23 mg and 0.46 mg QD PO.^{1,2}

6 STUDY POPULATION

Prospective approval of protocol deviations to the recruitment and enrollment criteria, also known as protocol waivers or exemptions, is not permitted.

6.1 Inclusion Criteria

Participants are eligible to be included in the study only if all of the following criteria apply:

1) Signed Written Informed Consent

- a) Participants must have signed and dated an Institutional Review Board (IRB)/Independent Ethics Committee (IEC)-approved written informed consent form (ICF) in accordance with regulatory, local, and institutional guidelines. This must be obtained before the performance of any protocol-related procedures that are not part of normal patient care.

2) Type of Participant and Target Disease Characteristics

- a) A diagnosis of UC, with signs and symptoms consistent with UC for at least 3 months prior to the first study intervention administration.
- b) Moderate to severely active UC disease activity, defined as a modified Mayo score of 4 through 9, inclusive, with the following minimum subscores:
 - i) An SF subscore ≥ 1 ,

AND

ii) An RB subscore ≥ 1 ,

AND

iii) An ES ≥ 2 (endoscopy performed within 60 days of the first study intervention administration).

- c) Must be up to date with screening for colorectal neoplasia and surveillance for dysplasia, according to local standard of care.
- d) Must have documentation of positive VZV IgG antibody status at screening or complete VZV vaccination prior to the first study intervention administration.
- e) Report of a previous colonoscopy that documents extent of disease (Note: If performed in the prior 60 days, this data may be used for study inclusion.)
- f) UC disease distribution (including ulcerative proctitis) extending proximal to the rectum (ie, approximately ≥ 5 cm from anal margin).

3) Age of Participant

- a) Participant must be over 18 years of age (or the legal age of consent in the jurisdiction in which the study is taking place) at the time of signing the informed consent.

4) Cohort 1 (Advanced Therapy-naïve Cohort): Disease Distribution and Prior UC Medication Exposure

In order to participate in Cohort 1, a participant must meet the eligibility criteria outlined in this inclusion criterion (IC) and must not meet the eligibility criteria outlined in IC 5.

- a) Participants must be naïve to 6-mercaptopurine/AZA and any biologics (see IC 5[a] for list) for any other medical indication, as well as UC.

5) Cohort 2 (Advanced Therapy-exposed Cohort): Disease Distribution and Prior UC Medication Exposure

In order to participate in Cohort 2, a participant must have failed only one mechanism of action of biologics.

- a) Documentation of an inadequate response, loss of response, or intolerance to a treatment course of one class of approved biologics (and should not have been treated with additional classes of approved biologics), including:
 - i) Anti-TNF agents (eg, infliximab, adalimumab, golimumab, certolizumab, anti-TNF biosimilars).
 - ii) Anti-integrin inhibitors (eg, vedolizumab).
 - iii) Anti-IL-12p40 biologics (eg, ustekinumab).
 - iv) Anti-IL-23p19 biologics (eg, mirikizumab, risankizumab).
 - v) Other biologics that may become approved for clinical use in this UC study during the course of the study (please discuss with Medical Monitor).
- b) Not Applicable Per Protocol Amendment 01: Patient may have been previously treated with 6-mercaptopurine/AZA, but not concomitantly over the course of the study, and not for at least 30 days prior to the first study intervention administration.

- c) Biologic agents should be discontinued at least 8 weeks prior or at least 5 elimination half lives prior to study intervention initiation, whichever is shorter. Washout period may be waived with the demonstration of absent drug levels on a therapeutic drug monitoring (TDM) assay.
- d) 6-mercaptopurine/AZA or methotrexate:
 - i) Participant may have been previously treated: with 6-mercaptopurine/AZA or methotrexate.
 - ii) Participant may not take these agents concomitantly over the course of the study.
 - iii) These agents must be discontinued prior to day of starting study intervention.

6) Dose Stabilization and Prohibited Concomitant Medications

- a) Compliance with the washout periods for prohibited concomitant medications, as listed in [Table 7.7-1](#).
- b) Must meet the dose stabilization criteria for permitted concomitant medications, as listed in [Table 7.7-3](#).

7) Reproductive Status

- Investigators shall counsel WOCBP participants on the importance of pregnancy prevention and the implications of an unexpected pregnancy.
- The investigator shall evaluate the effectiveness of the contraceptive method in relationship to the first dose of study intervention.
- Local laws and regulations may require the use of alternative and/or additional contraception methods.

a) Female Participants:

- i) Women who are not of childbearing potential are exempt from contraceptive requirements. Evidence to support this status must be included in source documents.
- ii) WOCBP must have a negative highly sensitive serum or urine pregnancy test (minimum sensitivity of 25 IU/L or equivalent units of human chorionic gonadotropin [hCG]) during the baseline as outline in the SOA ([Section 2](#)).
- The investigator is responsible for the review of medical history, menstrual history, and recent sexual activity to decrease the risk for inclusion of a woman with an early undetected pregnancy.
- iii) WOCBP must agree to follow the instructions for method(s) of contraception defined in [APPENDIX 4](#), as described below, and included in the ICF.
- iv) WOCBP are permitted to use hormonal contraception methods (as described in [APPENDIX 4](#)).
- v) A female participant is eligible to participate if she is not pregnant or breastfeeding, and at least one of the following conditions applies:
 - (1) Is not a WOCBP.
 - OR
 - (2) Is a WOCBP and using a contraceptive method that is highly effective (with a failure rate of < 1% per year), with low user dependency, as described in [APPENDIX 4](#), during the intervention period and for at least 90 days, and agrees

not to donate eggs (ova, oocytes) for the purpose of reproduction for the same time period.

6.2 Exclusion Criteria

Participants are excluded from the study if any of the following criteria apply:

1) Medical Conditions

- a) Recent (within 6 months of screening) myocardial infarction, unstable angina, stroke, transient ischemic attack, decompensated heart failure requiring hospitalization, or New York Heart Association Class III/IV heart failure.
- b) Presence of Mobitz type II second- or third-degree atrioventricular (AV) block, sick sinus syndrome, or sino-atrial block, unless the participant has a functioning pacemaker.
- c) Severe untreated sleep apnea.
- d) Current macular edema. (Note: Participants with diabetes, or a history of uveitis, retinal disease, or previous macular edema must have an ophthalmic evaluation of the fundus, including the macula, prior to the first study intervention administration.)
- e) Current active infection, and/or any infection requiring oral antibiotics within 14 days of screening, or intravenous (IV) antibiotics within 30 days of screening.
- f) Any major infection that required hospitalization.
- g) Immunodeficient state (not including previously mentioned immunosuppressants) leading to increased risk of opportunistic infections.
- h) A history of cancer within 5 years, including solid tumors and hematological malignancies (except basal cell carcinoma or squamous cell carcinoma of the skin that have been fully treated, or cervical dysplasia or carcinoma in situ that have been fully treated).
- i) Severe hepatic impairment (Child-Pugh Class C).

2) UC-related Exclusion Criteria

- a) Participant has a current diagnosis of Crohn's disease (CD), indeterminate colitis, radiation colitis or ischemic colitis, a monogenic cause of UC-like intestinal inflammation, colonic diverticulitis, or an alternative diagnosis that explains their colonic inflammation.
- b) Current or recent (within 3 months of screening) evidence of fulminant colitis, toxic megacolon, or bowel perforation.
- c) Current need for, or anticipated need for, surgical intervention for UC during the course of the study.
- d) Extensive colonic resection or current stoma.
- e) Colonic dysplasia that has not been removed.
- f) Previous or current use of JAK inhibitors (eg, tofacitinib, filgotinib).
- g) **Not applicable per Protocol Amendment 1:** UC involving the rectum only (UC proctitis).
- h) Women who are pregnant, planning on becoming pregnant during the study, breastfeeding, or who have a positive serum or urine beta-hCG test during screening or on Day 1.

3) Not applicable per Protocol Amendment 1: Reproductive Status

- a) Women who are pregnant, planning on becoming pregnant during the study, breastfeeding, or who have a positive serum or urine beta-hCG test during screening or on Day 1.

4) Prior/Concomitant Therapy

- a) Prior participation in an ozanimod clinical trial.
- b) Prior exposure to ozanimod or other S1P receptor modulators.
- c) Current immunomodulators for the treatment of UC.
- d) Previous or current JAK inhibitors for the treatment of UC.
- e) Current biologics for the treatment of UC.
- f) Current use of a monoamine oxidase inhibitor.
- g) Live or live-attenuated vaccine within 4 weeks prior to study intervention administration.
- h) Current or recent (without B cell recovery) use of alemtuzumab.
- i) Current use of beta interferon.
- j) Current use of glatiramer acetate.

Note: A detailed summary of prohibited concomitant medications and washout periods is listed in Table 7.7-1.

5) Physical and Laboratory Test Findings

If any of the following stool or blood tests were performed in the prior 30 days and can be documented, this data may be used for study inclusion.

- a) Evidence of organ dysfunction or any clinically significant deviation from normal in physical examination, vital signs, 12-lead ECGs, or clinical laboratory determinations beyond what is consistent with the target population.
- b) Positive stool test for *Clostridium difficile*. If positive, participants may be rescreened after appropriate treatment and retested no earlier than 7 days after completion of treatment.
- c) Positive stool test for pathogenic bacteria, ova, or parasites. If positive, participants may be rescreened after completion of treatment.
- d) Clinically significant abnormalities in laboratory testing during the screening period.
- e) Severe anemia (ie, hemoglobin [Hb] <8 g/dL) at screening visit.
- f) Liver function impairment or persisting elevations of aspartate aminotransferase (AST) or alanine aminotransferase (ALT) $> 2 \times$ upper limit of normal (ULN), or direct bilirubin $> 1.5 \times$ ULN.

6) Allergies and Adverse Drug Reaction

- a) Hypersensitivity to active ingredients or excipients of ozanimod.

7) Other Exclusion Criteria

- a) Prisoners or participants who are involuntarily incarcerated. (Note: Under certain specific circumstances and only in countries where local regulations permit, a person who has been imprisoned may be included or permitted to continue as a participant. Strict conditions apply, and Bristol-Myers Squibb [BMS] approval is required.)
- b) Inability to comply with study procedures, including study visits, venipunctures, endoscopies, etc.
- c) Participation in another clinical trial concurrent with this study.
- d) Any other sound medical, psychiatric, and/or social reason as determined by the investigator.

Eligibility criteria for this study have been carefully considered to ensure the safety of the study participants and that the results of the study can be used. It is imperative that participants fully meet all eligibility criteria. Further criteria will follow the product label.

6.3 Lifestyle Restrictions

Female participants (WOCBP only) should use highly effective contraception during the treatment period and for 90 days after discontinuing study intervention.

Aged, fermented, cured, smoked, and pickled foods containing large amounts of exogenous amines (eg, aged cheese, pickled herring) may cause release of norepinephrine, resulting in a rise of blood pressure (tyramine reaction). Consequently, participants will be counselled to avoid foods containing a large amount of tyramine during the treatment period.

6.4 Screen Failures

Screen failures are defined as participants who consent to participate in the clinical study but who are not subsequently entered in the study/included in the analysis population.

A minimal set of screen failure information is required to ensure transparent reporting of screen failure participants, to meet the Consolidated Standards of Reporting Trials publishing requirements, as applicable, and to respond to queries from regulatory authorities. Minimal information includes date of consent, demography, screen failure details, eligibility criteria, and any serious adverse events (SAEs).

6.4.1 Retesting During Screening or Lead-in Period

Participant re-enrollment: This study permits the re-enrollment of a participant who has discontinued the study as a pretreatment failure (ie, participant has not been treated). If re-enrolled, the participant must be re-consented and given a distinct patient identification number (PID).

Retesting of laboratory parameters and/or other assessments within any single screening or lead-in period will be permitted (in addition to any parameters that require a confirmatory value).

The most current result prior to the is the value by which study inclusion will be assessed, because it represents the participant's most current clinical state.

Laboratory parameters and/or assessments that are included in [Table 2-1](#), the SOA for Year 1, may be repeated in an effort to find all possible well-qualified participants. Discussion with the Medical Monitor is needed to identify whether repeat testing of any particular parameter is clinically relevant.

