FSH ^f	X							Optional. See footnotes
TDM Test ^g	X							Optional. See footnotes
Diagnostic Test for SARS-CoV-2	X							Participants must have a negative SARS-CoV-2 PCR test result prior to Day 1, in accordance with site standard practices
Stool Collection								
For Clostridium difficile Testing (and stool infectious screen)	X						x ^h	Stool test results from anytime within 30 days prior to starting first dose of study intervention can be considered for screening process. Results must be documented, if obtained locally.

Table 2-1: Schedule of Activities for Year 1 (IM047029)

Procedure	Screening (Days -28 to -1)	Week 0 (Day 1)	Week 4 (Day 28)	Week 12 (Day 84)	Week 26 (Day 182)	Week 52 (Day 365)	Unscheduled ^a	Notes
Visit Window (± n Days)			7	7	7	14		
For Culture, Ova, and Parasites ⁱ	X							or stool PCR - see footnotes
Endoscopy and Biopsies^j								
Cohort 1 (Advanced Therapy-naïve Cohort)	X			X				Results from endoscopy (colonoscopy or sigmoidoscopy) performed within 60 days prior to first dose of study intervention may be considered for the screening process. Images must be documented to confirm severity. In the setting of historic (prior) endoscopy documentation, biopsy tissue will not be collected.
Cohort 2 (Advanced Therapy-exposed Cohort)	X				X			Results from endoscopy performed within 60 days prior to first dose, may be considered for the screening process. Images must be documented to confirm severity. In the setting of historic (prior) endoscopy documentation, biopsy tissue will not be collected.
Additional Efficacy Assessments^k								
Site Calculates Modified Mayo Score	X			X ^l	X ^m			Required for eligibility assessment

Table 2-1: Schedule of Activities for Year 1 (IM047029)

Procedure	Screening (Days -28 to -1)	Week 0 (Day 1)	Week 4 (Day 28)	Week 12 (Day 84)	Week 26 (Day 182)	Week 52 (Day 365)	Unscheduled ^a	Notes
Visit Window (± n Days)			7	7	7	14		
Baseline (prior to flare) SF	X							
PGA Collection	X	X	X	X	X	X		Physician-reported
RB Subscore	X	X	X	X	X	X		Recorded for 7 days prior to Day 1, daily for the first 12 weeks of the study, and 7 days prior to each study visit thereafter
SF Subscore	X	X	X	X	X	X		
HRQOLⁿ								
IBDQ		X	X	X	X	X		

Table 2-1: Schedule of Activities for Year 1 (IM047029)

Procedure	Screening (Days -28 to -1)	Week 0 (Day 1)	Week 4 (Day 28)	Week 12 (Day 84)	Week 26 (Day 182)	Week 52 (Day 365)	Unscheduled ^a	Notes
Visit Window (± n Days)		7	7	7	14			
Healthcare Resource Utilization^b								

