10.4.1 General Considerations

Baseline is defined as the last observed measurement prior to the first dose of study intervention on Day 1.

In general, descriptive summaries will be presented for the efficacy and safety variables collected. Continuous variables will be summarized using the number of participants (n), mean, standard deviation, minimum, median, and maximum. Categorical variables will be summarized using frequency counts and percentages, and 95% CIs. Analyses will be performed separately for each cohort, unless otherwise stated.

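### Section 6.4.1 permits discretionary repeats of the SF, RB and modified Mayo entry scores with no stated limit, so participants who qualify on a repeat can add a small, avoidable upward bias to the uncontrolled response rate

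*Combined protocol and SAP*

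**What the plan says.** Section 6.4.1 is not confined to laboratory tests: "Retesting of laboratory parameters and/or other assessments within any single screening or lead-in period will be permitted". It adds that parameters and assessments in Table 2-1 "may be repeated in an effort to find all possible well-qualified participants", and that the most current result "is the value by which study inclusion will be assessed". The check on this is in the same paragraph: "Discussion with the Medical Monitor is needed to identify whether repeat testing of any particular parameter is clinically relevant". No criteria for that discussion and no maximum number of repeats are given. A further route is open after a failed screening: "This study permits the re-enrollment of a participant who has discontinued the study as a pretreatment failure", with new consent and a new identification number.

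Table 2-1 has a row "Site Calculates Modified Mayo Score", marked before dosing only at Screening (Days -28 to -1). The SF and RB rows are marked at Screening and again at Day 1, with the diary covering the 7 days before Day 1. Inclusion criterion 2b requires active disease "defined as a modified Mayo score of 4 through 9, inclusive, with the following minimum subscores", namely SF at least 1, RB at least 1 and endoscopic subscore (ES) at least 2.

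Section 10.4.1 states: "Baseline is defined as the last observed measurement prior to the first dose of study intervention on Day 1". The primary endpoint (Table 10.4.3-1) is a fall from baseline in the modified Mayo score. Section 10.1 confirms that there is no control group and no hypothesis testing.

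**The concern.** The score that admits a participant is also the score whose later fall defines success. SF and RB vary from week to week. If a participant who misses criterion 2b can be measured again, those who enter on a repeat are more often people whose usual level lies below the threshold and who happened to have a worse week. Some will drift back without any drug effect, and the endpoint will count part of that drift as clinical response.

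A control arm would show the same drift and allow it to be subtracted. Here the response rate and its exact interval stand alone. The interval covers sampling error only, so a systematic upward shift would not show in it.

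**Working it through.** **Inputs from the protocol.** Entry: SF ≥ 1, RB ≥ 1, ES ≥ 2, total 4 to 9 (Section 6.1, 2b). Response: fall of at least 2 points and at least 35%, with an RB fall of at least 1 or RB ≤ 1 (Table 10.4.3-1). Planned precision: 50% of 150 and 45% of 100 (Section 10.2). The documents give no test-retest reliability, so every bias figure below is conditional on assumptions.

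**Step 1: the plan's own figures.** The Clopper-Pearson limits are the 2.5% quantile of Beta(x, n-x+1) and the 97.5% quantile of Beta(x+1, n-x).
- Cohort 1, 75/150: 41.74% to 58.26%, half-width 8.26 points. This reproduces the stated 41.7% to 58.3%.
- Cohort 2, 45/100: 35.03% to 55.27%, half-width 10.12 points. This reproduces the stated interval of 35% to 55.3%.

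**Step 2: can drift alone meet the endpoint?** Entry at SF 1 + RB 1 + ES 2 = 4. Later SF 0 + RB 0 + ES 2 = 2. The fall is 2 points, 2/4 = 50%, with RB ≤ 1. All three conditions are met with ES unchanged. This path needs no repeat; a first-attempt entrant can follow it too.

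**Step 3: what repeats add if the qualifying week is baseline.** Simulation with no drug effect, 600,000 virtual patients per run. Assumptions: latent SF, RB and ES are normal with means 1.3, 1.3 and 1.9, SDs 0.9, 0.9 and 0.8, and pairwise correlation 0.5. Measurement noise is added, and readings are rounded and limited to 0 to 3. Every patient who fails repeats SF and RB only; the endoscopy is kept.

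| Reliability SF, RB / ES | Repeats allowed | Entered on a repeat | Chance response: first-pass | Repeat-qualified | All | Added (all minus first-pass) |
|---|---|---|---|---|---|---|
| 0.9 / 0.9 | 1 | 6.7% | 2.4% | 11.5% | 3.0% | 0.6 |
| 0.9 / 0.9 | 3 | 10.6% | 2.4% | 14.2% | 3.7% | 1.3 |
| 0.7 / 0.8 | 1 | 11.6% | 6.6% | 16.8% | 7.8% | 1.2 |
| 0.7 / 0.8 | 3 | 17.1% | 6.7% | 19.5% | 8.8% | 2.1 |
| 0.5 / 0.7 | 1 | 15.4% | 10.9% | 19.5% | 12.2% | 1.3 |
| 0.5 / 0.7 | 3 | 21.7% | 10.8% | 22.4% | 13.4% | 2.6 |
| 0.7 / 0.8, milder (SF, RB mean 0.9) | 3 | 27.7% | 9.4% | 22.7% | 13.1% | 3.7 |

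Check: added = share on a repeat × (repeat-qualified rate − first-pass rate). For 0.7 / 0.8 with three repeats, 0.171 × (19.5 − 6.7) = 2.2, which agrees with 2.1 within rounding.

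A second model holds ES unchanged (2 or 3, equally likely), with mean SF 1.0 to 1.5, mean RB 0.7 to 1.2, SD 0.9 and reliability 0.5 to 0.9. Up to three repeats add 0.6 to 2.6 points; a single repeat at the favourable end adds 0.3. Together the two models give about 0.3 to 2.6 points, apart from the milder population.

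**Step 4: what repeats add if Day 1 is baseline.** Draw a fresh Day 1 SF and RB reading and use it as baseline. In the second model the addition falls to about 0.1 to 0.4 points, because most SF/RB regression then happens before baseline. In the first model the same change leaves about 0.2 points (1.7% to 1.9%; reliability 0.9 / 0.9, one repeat) to 1.2 points (6.8% to 8.0%; reliability 0.6 / 0.7, three repeats). It leaves more because the noisy screening ES still serves as both entry and baseline reading. The 0.1 to 0.4 figure therefore assumes a stable ES.

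**Step 5: scale.** 2.6% of 150 is 3.9 participants and 2.6% of 100 is 2.6; 0.3% of 150 is 0.45. In the table rows, the chance response present without any repeat is most of the total: 2.4/3.7 = 65%, 6.7/8.8 = 76% and 10.8/13.4 = 81% with three repeats.

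**The case against.** Three points against the concern are sound.

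First, a reader might infer that a site may re-measure until the participant qualifies. The text does not say that. A Medical Monitor discussion is required, screening runs from Day -28 to Day -1, and the most current result decides rather than the best, so a later low reading disqualifies. What remains is that the discussion has no criteria, the number of repeats has no stated limit, and the disease-activity scores are not excluded.

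Second, a reader might infer that the high qualifying week is necessarily the baseline. That is not established. SF and RB are scheduled again at Day 1, and the last pre-dose value is baseline. Equally, the modified Mayo score is calculated before dosing only at Screening, and the only pre-dose diary window stated is the 7 days before Day 1, so entry and baseline may rest on the same data. The protocol does not say which SF and RB readings form the baseline score, and the size of the bias depends mainly on this.

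Third, the cause could be misattributed. Most chance response, including the drift from 4 to 2 in Step 2, follows from entry by threshold in an uncontrolled study. Removing repeats leaves it in place.

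The simulations also retest every patient who fails, which Medical Monitor review makes unlikely. Re-enrolment at a genuine later flare is legitimate in a relapsing disease and is not a fault in itself.

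**Conclusion.** The concern holds in direction and is modest in size. Section 6.4.1 as written covers the scores that define both entry and the primary endpoint, and any resulting bias is upward and cannot be separated from drug effect in this design.

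If the qualifying diary week is baseline, one to three repeats add about 0.3 to 2.6 points, or up to 3.7 in a milder screened population. If the Day 1 reading is baseline, the addition is about 0.1 to 0.4 points with a stable ES, and somewhat more if endoscopic scoring is also noisy. All of this is below the interval half-widths of 8.3 and 10.1 points. The figures rest on assumed reliability, means and SDs and on retesting every patient who fails; they show a plausible range and are not an estimate for this trial. The documents do not support reading the response rate as largely a product of retesting. The case for change is that the bias is systematic, outside what the interval covers, and cheap to remove or expose.

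**What to change.** In Section 6.4.1, do one of the following:

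1. Limit discretionary within-period retesting to laboratory, stool, pregnancy, ECG and other safety or eligibility tests, and expressly exclude SF, RB, ES and the modified Mayo score.
2. If repeats of these scores are kept, flag each one in the eCRF and report the primary response rate with and without participants who qualified on a repeat.

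In either case, state in Section 10.4.1 that baseline SF and RB come from one diary window for all participants, the 7 days before Day 1. If that same window also decides entry, this sentence alone does not reduce the bias, and option 1 or 2 is still needed.

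Do not use a different baseline, such as an average over all pre-dose weeks, only for participants with repeats: that would put two baseline definitions into one endpoint. No cap on re-enrolment is needed.

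Cost: a sentence or two of text, plus slightly more screen failures under option 1, or one eCRF flag and one sensitivity analysis under option 2.
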